The proposed study is a 28-week randomized, placebo-controlled, double-blind trial comparing the efficacy of ACTH versus placebo for the treatment of fatigue in patients with RMS (RMS). Ninety patients with RMS who meet all of the eligibility criteria will be enrolled from five participating sites. Eligible patients will be consented by site investigators or delegated research personnel before undergoing any study procedures. Subjects will be randomized to ACTH or placebo at 1:1 ratio.

Endpoints

The primary objective of this study is to assess the efficacy of ACTH versus placebo in reducing fatigability in patients with relapsing MS. The primary endpoint is a statistically significant reduction of fatigue measured by MFIS and FSS, which will be administered at baseline, week 8, 16, 24, and 28.

Secondary objectives include assessment of the tolerability and safety of weekly ACTH treatment vs. placebo and evaluation of ACTH on depression, sleepiness, and quality of life measures and the correlations between measures. The secondary endpoints are measured by BDI-II, ESS, SF-36 at baseline, week 8, 16, 24, and 28. Clinical and laboratory adverse events (AE) and serious adverse events (SAE) will be monitored continuously during the study period to capture safety and tolerability information.

Patient Recruitment

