Patients with stable (no relapses for the previous 90 days) relapsing form of MS, being treated with interferon beta1a or 1b, glatiramer acetate, fingolimod, dimethyl fumarate or teriflunomide for at least 6 months, with Expanded Disability Status Scale (EDSS) scores of 4 or less, Modified Fatigue Impact Scale (MFIS) score of 38 or greater, or a Fatigue Severity Scale (FSS) score of 36 or greater, Beck Depression Inventory-II (BDI-II) score of 19 or less, and Epworth Sleep Score (ESS) of 9 or less. Subject will be excluded if he or she has attempted suicide in the past, has current suicidal thinking based on the Columbia Suicide Severity Rating Scale (C-SSr), or is preparing for suicide. History must be negative for difficulty sleeping, sleep apnea, painful nocturnal spasms, nocturnal neuropathic pain, and restless leg syndrome, history of psychosis or neuroleptic use, have no evidence of current hypothyroid state, use of cannabis, opiates, benzodiazepines, or other gaba-ergic medications except baclofen or tizanidine. Subjects cannot have received corticosteroids of any type for 90 days prior to baseline visit. Subjects must not have any of the contraindications for Acthar Gel as listed in the approved label, including sensitivity to proteins of porcine origin. Subject must agree not receive any live or live-attenuated vaccine during the trial. Ninety subjects will be recruited and randomized 1:1 to receive ACTH or placebo in a subject and examining physician-blinded manner. The sample size was calculated by a power analysis for a two-sided test with $\alpha=0.05$ and power = 0.80 and assuming a 20% dropout rate.

Subjects will be randomized in groups of 4, with equal number of placebo and ACTH treated patients in each 4-subject group. In order to reach enrollment target in 12 months, full competitive enrollment will be applied until the enrollment goal is fulfilled.

The study protocol, informed consent forms (ICF), and case report forms (CRF) must be approved by the organization's institutional review board or appropriate ethics committee. Site investigators will obtain written informed consent to participate from eligible patients prior to screening or any study procedures taking place. A copy of the ICF will be given to the patient and the original ICF and the documentation of the consent process will be kept in the patient's record at each site.

Inclusion Criteria

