Data forms will be faxed to the data coordination center within 3 business days after each study visit and processed by staff trained in data entry procedures. The forms will be entered by two staff working independently. The completeness of the data and whether the data values are in an appropriate range will be checked periodically. Study sites will be asked to complete data clarification requests for confirmation of missing data or questionable information.

Statistical/Analytical Plan

Primary endpoint

Statistical analysis will be performed to test the change from baseline to end of study in two fatigue measures (MFIS and FSS) to be completed by patient at baseline, Week 8, Week 16, Week 24, and Week 28.

Secondary endpoint

Statistical analysis will be done to test the change from baseline to end of study in depression, sleepiness, and quality of life measures (BDI-II, ESS, and SF-36) to be completed by patient at baseline, Week 8, Week 16, Week 24, and Week 28.

All AEs are to be coded and grouped by organ system. AEs will also be tabulated by severity and by relationship and summarized by treatment group. Summary tables of the AEs will be presented to show the incidence and frequency by treatment group and by study site.

Statistical method

This study will collect longitudinal data that consists of repeated measures on each individual. The mixed-effects regression model for the analysis of longitudinal data will be used to test the changes of the fatigue scores over time.

Sample Size Justification

Ninety subjects will be recruited and randomized 1:1 to receive ACTH or placebo in a subject and examining physician-blinded manner. If the MFIS score decreases from 38 for about 20% with standard deviation =16.4 in the 45 patients who received ACTH, the power to reject the null hypothesis in a paired t-test with alpha=0.5 would be 86%. If the difference of the changes of MFIS score between two treatment group is 7.6 with within group standard deviation=16.4 in the 90 patients, the power to reject the null hypothesis in a t-test with alpha= 0.5 would be 87%. Ziemssen and colleagues (Ziemssen, Hoffman, Apfel, & Kern, 2008) studied the effect of glatiramer acetate on fatigue in MS patients. Glatiramer acetate was found to be associated with a reduction in absence from work and a significant reduction in fatigue symptoms, as measured by MFIS. The data from Ziemssen et al. were used for the sample size calculation for this study.

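### The Sample Size Justification prints alpha as 0.5 for both t-tests, against two-sided 0.05 in Patient Recruitment; correcting it also requires restating the 87% two-group power

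*Combined protocol and SAP*

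**What the plan says.** Section C of the combined protocol and SAP describes the sizing of the trial in two places.

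- **Patient Recruitment** attributes the 90 subjects to a "power analysis for a two-sided test with $\alpha=0.05$ and power = 0.80 and assuming a 20% dropout rate".
- **Sample Size Justification**, under Statistical/Analytical Plan, gives two scenarios. The first is within the ACTH arm: "If the MFIS score decreases from 38 for about 20% with standard deviation =16.4 in the 45 patients who received ACTH", with the result "the power to reject the null hypothesis in a paired t-test with alpha=0.5 would be 86" per cent. The second is between arms: "If the difference of the changes of MFIS score between two treatment group is 7.6 with within group standard deviation=16.4 in the 90 patients", with the result "the power to reject the null hypothesis in a t-test with alpha= 0.5 would be 87" per cent.

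The Endpoints section makes success depend on significance: "The primary endpoint is a statistically significant reduction of fatigue measured by MFIS and FSS". The planned analysis, under Statistical method, is a mixed-effects regression model for repeated measures, and no significance level is attached to it. The Primary endpoint and Secondary endpoint paragraphs of the Statistical/Analytical Plan give none either.

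**The concern.** The two sections describe one sizing exercise and give levels that differ by a factor of ten. They cannot both be right, and a reader cannot check either power figure until the level is settled.

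The level also matters beyond the sizing. The primary endpoint is worded as a statistically significant reduction, yet the plan never says at what level the primary analysis will be tested. The only level printed inside the Statistical/Analytical Plan is the erroneous 0.5, and the 0.05 in Patient Recruitment is tied to the power analysis only.

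**Working it through.** **Inputs**

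- Effect: 20% of 38 = 7.6 MFIS points for the paired test; a difference of 7.6 is stated for the two-group test (Sample Size Justification).
- SD: 16.4 (same section), taken as the SD of the change.
- Patients: 45 on ACTH; 90 in total at 1:1, so 45 per arm (same section).
- Dropout: 20% (Patient Recruitment), so 45 × 0.8 = 36 completers per arm.
- Level: 0.5 (Sample Size Justification) or two-sided 0.05 (Patient Recruitment).

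**Method.** Power is the two-sided non-central t probability of exceeding the critical value t(1 − alpha/2, df). The non-centrality parameter is (7.6/16.4) × √n for the paired test, with n − 1 df. For the two-group test it is 7.6 / (16.4 × √(2/n)) with n per arm and 2n − 2 df. The standardised effect is 7.6/16.4 = 0.463.

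**Step 1: the stated 86%, paired test, n = 45.** Non-centrality = 0.463 × √45 = 3.109, with 44 df.

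| Two-sided alpha | Critical t | Power |
|---|---|---|
| 0.05 | 2.015 | 86.0% |
| 0.5 | 0.680 | 99.2% |

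Solving for the two-sided alpha that gives exactly 86% returns 0.0500. The plan's own figure therefore identifies 0.05 as the level used.

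**Step 2: the stated 87%, two-group test.** With 45 per arm the standard error is 16.4 × √(2/45) = 3.457 and the non-centrality is 7.6/3.457 = 2.198, with 88 df.

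| Patients per arm | Power at 0.05 | Power at 0.5 |
|---|---|---|
| 45 | 58.5% | 93.8% |
| 36 | 49.2% | 90.5% |
| 90 | 87.1% | 99.3% |

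With 45 per arm, the alpha that would give 87% is 0.286, which is neither printed value. The 87% appears at 0.05 only with 90 per arm, as if the total of 90 had been entered as the size of each arm.

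**Step 3: sensitivity to the SD assumption.** If 16.4 were the SD of a single score and visits were uncorrelated, the SD of the change would be 16.4 × √2. The paired power would then be 57.5% at 0.05 and 93.8% at 0.5. The 0.5 still does not give 86%.

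**Step 4: sensitivity to sidedness and completers.** A one-sided 0.05 test with 36 completers also gives 86.0% for the paired test. The text says 45 patients and a two-sided test, and this alternative also points to 0.05.

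**The case against.** The strongest reply is that this is a typographical slip that the document largely corrects itself. Patient Recruitment prints 0.05, the 86% solves back to 0.0500, and a statistician would recognise the error at once. Much of that stands. It limits the seriousness of the point, but it does not remove two wrong figures from the current text.

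A reader might infer more: that the plan declares significance at p < 0.5, with a 50% false-positive rate per test. The documents do not support this. Both 0.5 values are inputs to hypothetical t-test power statements under Sample Size Justification, and the planned analysis is a mixed-effects model with no level attached. Nor can the 0.05 be set aside as being only for sizing while the 0.5 is treated as the trial's rule, because both belong to the sizing. The accurate statement is that the plan gives no level for its primary analysis.

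A reader might also infer that both printed powers are correct once alpha is read as 0.05. Only the 86% is correct with the stated patient numbers.

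A last objection concerns the remedy. Changing the second alpha and nothing else would leave 87% power claimed at 0.05 in 90 patients, replacing an obvious misprint with a plausible but false sentence. This objection stands in full, and the fix allows for it.

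**Conclusion.** The point holds as an error in the inputs to the stated power. The 0.5 in the Sample Size Justification contradicts the two-sided 0.05 in Patient Recruitment, and the paired-test figure shows that 0.5 was not the level used (86.0% at 0.05, 99.2% at 0.5). The exact match assumes that 16.4 is the SD of the change; the rejection of 0.5 does not depend on that assumption.

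The 87% cannot be reconciled with either level at 45 per arm. At two-sided 0.05 the two-group power is 58.5%, a shortfall of 87 − 58.5 = 28.5 percentage points, and 49.2% with 36 completers per arm. That the 87% came from using 90 per arm is an inference from the match at 87.1%; the documents do not say so.

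Separately, no significance level is stated for the primary mixed-effects analysis, although the endpoint is defined by significance. That is an omission, and it should not be read as a 50% error rate.

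**What to change.** 1. In the Sample Size Justification, replace both printed values of 0.5 with two-sided alpha = 0.05.
2. In the same edit, restate the two-group power as about 58% with 45 per arm, and about 49% with 36 completers per arm after the 20% dropout given in Patient Recruitment. State that 16.4 is taken as the SD of the change.
3. Under Statistical method, add one sentence giving two-sided 0.05 as the level for the primary analysis. Whether both or either of MFIS and FSS must reach it is a separate question that this sentence does not settle.

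The cost is two corrected alphas, one rewritten power statement and one added sentence, with no change to design or conduct from the edit itself. The corrected two-group power will be visibly below the 0.80 given in Patient Recruitment, and the sponsor will have to address that gap separately.

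### The stated 87% power for the ACTH-placebo comparison is wrong: 45 per arm gives 58%, and 49% after the planned 20% dropout; 87% needs 90 patients per arm.

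*Combined protocol and SAP*

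**What the plan says.** Two sections of part C deal with sample size.

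- **Sample Size Justification** (Statistical/Analytical Plan). Ninety subjects are randomised 1:1. Two calculations follow, both with SD 16.4. The first is a within-arm test: if MFIS falls by about 20% from 38 in the 45 ACTH patients, "the power to reject the null hypothesis in a paired t-test with alpha=0.5 would be 86" percent. The second compares the arms: "If the difference of the changes of MFIS score between two treatment group is 7.6", with the same SD, then "in the 90 patients, the power to reject the null hypothesis in a t-test with alpha= 0.5 would be 87" percent. The inputs are attributed to a published study of glatiramer acetate and fatigue.
- **Patient Recruitment.** "The sample size was calculated by a power analysis for a two-sided test" at alpha 0.05, with "power = 0.80 and assuming a 20% dropout rate". No difference or SD is given here.

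The section on the premature termination visit adds that randomised patients who withdraw are not replaced. Under Statistical method, the planned analysis is a mixed-effects regression on the repeated scores.

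**The concern.** The two power figures are almost equal, 86% and 87%. One is a paired test in 45 patients and the other compares two arms of 45, with the same difference and the same SD. That cannot be right. The standard error of a difference between two independent arms is larger by a factor of √2 than that of a mean change in one arm of the same size, so power must be clearly lower.

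The second figure is the only power statement for the trial's primary objective, ACTH versus placebo. If it is too high, ethics committees, the DSMB and later readers will take a null result as coming from a well-powered trial. The alpha printed twice as 0.5 also conflicts with the 0.05 under Patient Recruitment, and the 80% power with 20% dropout stated there is a third figure to reconcile.

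**Working it through.** **Inputs**

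| Quantity | Value | Source |
|---|---|---|
| Difference in MFIS change, δ | 7.6 (= 0.20 × 38) | Sample Size Justification |
| SD, σ | 16.4 | Sample Size Justification |
| Randomised | 90, 1:1, so 45 per arm | Sample Size Justification |
| Test level | two-sided 0.05 | Patient Recruitment |
| Dropout | 20%, so 0.8 × 45 = 36 per arm | Patient Recruitment |
| Replacement | none | Premature termination visit |

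**Formulas.** Power is P(|T| > t*), where T is noncentral t and t* is the two-sided critical value.

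- Paired, n patients: λ = δ / (σ/√n), df = n − 1.
- Two arms of n: λ = δ / (σ√(2/n)), df = 2n − 2.

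**Step 1: the figure that reproduces.** Paired, n = 45: SE = 16.4/√45 = 2.445; λ = 7.6/2.445 = 3.109; df = 44; t* = 2.015. Power is **86.0%**, as printed. The authors therefore worked at two-sided 0.05 and used 16.4 as the SD of the change.

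**Step 2: the between-arm figure as designed.** 45 per arm: SE = 16.4 × √(2/45) = 3.457; λ = 7.6/3.457 = 2.198; df = 88; t* = 1.987. Power is **58.5%** (59.4% by the normal approximation), not 87%.

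**Step 3: where 87% comes from.** 90 per arm: SE = 16.4 × √(2/90) = 2.445; λ = 3.109; df = 178; t* = 1.973. Power is **87.1%**. The noncentrality equals that in Step 1 because 2/90 = 1/45, and only the degrees of freedom differ. That is why the two printed figures are one point apart.

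**Step 4: with the planned dropout.** 36 per arm: SE = 16.4 × √(2/36) = 3.866; λ = 1.966; df = 70; t* = 1.994. Power is **49.2%**.

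**Step 5: other readings of the printed numbers.**

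| Reading | Power | Printed |
|---|---|---|
| 45 per arm, alpha 0.5 two-sided | 93.8% | 87% |
| Paired n = 45, alpha 0.5 two-sided | 99.2% | 86% |
| 45 per arm, one-sided 0.05 | 70.4% | 87% |

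An alpha of 0.5 reproduces neither figure, so it is a misprint. A one-sided test contradicts Patient Recruitment and still falls short.

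**Step 6: what 90 patients can detect, and what 7.6 needs** (two-sided 0.05).

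- Difference detectable with 80% power at SD 16.4: **9.8** points (45 per arm) or **11.0** (36 per arm).
- For 87% at 45 per arm: an SD of about 11.6 or a difference of about 10.8.
- For 80% at a difference of 7.6: 75 evaluable per arm; 75/0.8 = 93.75, so 94 per arm or 188 randomised.

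**Step 7: the 80% under Patient Recruitment.** That section gives no difference or SD, so this step assumes 7.6 and 16.4 apply there too. Ninety per arm less 20% is 72 per arm, which gives 78.9%, close to 80%. The actual 36 per arm gives 49.2%. Both between-arm claims fit a trial of 180; neither fits 90.

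**The case against.** The strongest objection is that the trial will not be analysed by a t-test on a single change score. A mixed model uses the baseline and four later visits, and patients who leave early still contribute interim scores and an MFIS at the termination visit. Its power could exceed 58%, and 49% treats dropouts as contributing nothing. For illustration only: if the repeated data cut the effective variance by 10% to 40%, power at 45 per arm would be about 63% to 80%. This stands as a limit on how the figures are read: 49% is the completers-only case, and neither figure is the power of the mixed model. It does not rescue the 87%, which is stated for a t-test. The documents give no correlation from which a gain could be calculated, and even a 40% reduction does not reach 87%.

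A second objection is that 16.4 may be the SD of a score rather than of a change. A baseline-to-follow-up correlation of about 0.75 would then give 86.7% for a change-score analysis. But no correlation is stated, the text attaches the SD to the changes, and the paired 86% reproduces with 16.4 as the SD of change.

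Two smaller points are fair. That the total was entered as the per-arm size is an inference from a numerical match, not something the documents state. And the like-for-like overstatement is 87 − 58.5 = 28.5 points; the gap of 87 − 49.2 = 37.8 points sets a figure with dropout against one without.

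**Conclusion.** The concern holds. For the t-test the plan describes, power is 58.5%, not 87%, an overstatement of 28.5 percentage points. With the protocol's own dropout and completers only, it is 49.2%, which is 30.8 points below the 80% under Patient Recruitment if that sentence rests on the same difference and SD. On that test a true 7.6-point benefit would be missed in about 42% of trials with full follow-up and about 51% with 36 per arm.

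This rests on a two-sided 0.05 level, 16.4 as the SD of change and equal arms. The documents state the level and the allocation, and the reproduced paired figure confirms the level and the reading of the SD. The paired figure itself does not support the sample size: with no comparator, it cannot separate a drug effect from placebo response or from regression to the mean in patients selected for high fatigue scores.

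**What to change.** 1. In Sample Size Justification, replace the between-arm sentence with: 45 per arm, two-sided alpha 0.05, difference 7.6 and SD of change 16.4 give 58% power for a t-test (49% if 20% drop out and contribute no data); the difference detectable with 80% power is 9.8 points (11.0 with dropout).
2. Correct alpha from 0.5 to 0.05 in both places.
3. In Patient Recruitment, replace the 80% power and 20% dropout statement with the same figures.
4. Remove the paired test as support for the sample size. If it is kept for information, say that it does not bear on ACTH versus placebo.
5. If the sponsor expects the mixed model to do better, give its power with the assumed correlation, visit-wise dropout and source. If 80% at 7.6 points is to remain the target, the t-test inputs require about 188 randomised.

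Items 1 to 4 change wording only and add no patients or procedures. The cost is an amendment, which under Regulatory Requirements needs approval by the coordinating IRB and by each site's committee, and a less favourable stated power. The larger sample in item 5 is an option for the sponsor and is not needed to correct the error.

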1. Patient has a relapse during the study. A relapse is defined as a new symptom, or worsening of pre-existing neurologic symptoms, of at least 24 hours duration, in patients who had been clinically stable for the prior 30 days, in the absence of fever, sleep deprivation or severe emotional stress.
2. Patient has an adverse event that presents unacceptable risk judged by the investigator
3. Patient has inadequate adherence to the protocol
4. Patient is lost to follow-up
5. Patient becomes pregnant

Treatment Overview**Dosage and Administration of Acthar® or matching placebo**

The study drug (ACTH 40 units or identical-appearing placebo) will be given subcutaneously twice weekly for 2 weeks. If the patient tolerates this dosage regimen, the dose will be increased to 80 units or placebo twice weekly. If the 80 unit dosage is not tolerated, the dosage will be reduced to 40 units twice weekly for the remainder of the 24 week participation. The weekly doses will be given 3 days apart, for example, on every Monday and Thursday or every Tuesday and Friday. Patients are not allowed to take doses on consecutive days. If a patient cannot take a dose on a scheduled day, the dose can be taken either a day early, or a day late. Patients that forget to take their scheduled dose will be encouraged to take their dose the following day.

Randomization/Treatment assignment and blinding

A total of 90 patients will be randomized either to active drug (ACTH), or placebo in a 1:1 ratio stratified by study site. Each study site will be assigned a site number, and each patient who signed consent form and received a screening test will have a unique study ID, which identifies the patient and the study site at which they participate throughout the study. Within each site, subjects will be randomized in blocks of 4, 2 ACTH and 2 placebo treated patients, to achieve balance in the allocation of subjects to study drug versus placebo arms. The order in which each of the 4 samples is selected will be predetermined by a

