The following clinical and laboratory evaluations will occur 16 weeks after baseline with a +/- 4 day window. The investigator/treating neurologist will review inclusion/exclusion criteria to confirm patient eligibility before study drug is dispensed.

- Interval medical and neurological history
- Vital signs
- Physical and neurological exam
- Laboratory assessments: CBC, Urinalysis, CMP, Pregnancy test/HCG (female only)
- MFIS, FSS, BDI-II, ESS, SF36, C-SSR*
- Study drug dispensing
- Protocol compliance study drug accountability
- Concomitant therapy and AEs
- Additional serum sample for research purposes

* The C-SSR must be reviewed by the site principal investigator or treating physician prior to the patient leaving the clinic

Visit 5/Week 24 (24 weeks +/- 4 days from baseline)

The following clinical and laboratory evaluations will occur 24 weeks after baseline with a +/- 4 day window. The investigator/treating neurologist will review inclusion/exclusion criteria to confirm patient eligibility.

- Interval medical and neurological history
- Vital signs
- Physical and neurological exam
- Laboratory assessments: CBC, Urinalysis, CMP, Pregnancy test/HCG (female only)
- MFIS, FSS, BDI-II, ESS, SF36, C-SSR*
- Protocol compliance study drug accountability
- Concomitant therapy and AEs

- Additional serum sample for research purposes

* The C-SSR must be reviewed by the site principal investigator or treating physician prior to the patient leaving the clinic

Visit 6/Week 28 (28 weeks +/- 4 days from baseline)

The following clinical and laboratory evaluations will occur 28 weeks after baseline with a +/- 4 day window.

- Interval medical and neurological history
- Vital signs
- Physical and neurological exam
- Laboratory assessments: CBC, Urinalysis, CMP
- MFIS, FSS, BDI-II, ESS, SF36, C-SSR*
- Protocol compliance study drug accountability
- Concomitant therapy and AEs
- Additional serum sample for research purposes

* The C-SSR must be reviewed by the site principal investigator or treating physician prior to the patient leaving the clinic

Premature termination visit

If discontinuation of study drug occurs, a premature termination visit must be performed as soon as possible, or within 7 days after the last dose of study drug. Randomized patients who were withdrawn from the study for any reason will not be replaced. The following clinical and laboratory evaluations will be performed:

- Interval medical and neurological history
- Vital signs

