D. REGULATORY, SAFETY AND MONITORING

Members and Responsibilities of DSMB

There will be 3 members of the DSMB, one will be a clinical neurologist with expertise in the treatment of patients with MS, one will be a PhD level biostatistician with past experience in statistical analysis of clinical studies of MS and one will be a physician with adequate expertise in endocrinology. The DSMB will review all adverse events (including all MS relapses) that occur during the study, independently conduct the interim analysis, the timing of which as described above, and the final analysis for safety and efficacy of the investigational treatment. The DSMB will also meet at any time they may choose if there are concerns for patient safety. Records of all committee reviews and input will be kept in the study binder.

Regulatory Requirements

The study will be performed in accordance with ICH GCP Guidelines and the Code of Federal Regulations for clinical research. Any amendments to the study protocol must be approved by Providence IRB and the IRB/IEC of each site before implementation. AEs and protocol violations or deviations must be reported according to the guideline of the IRB/IEC of each site.

Safety Assessments

Physical Examination

A full physical examination will be conducted at every visit. Any worsening or new abnormality that is clinically significant is to be recorded as an AE and will be analyzed as such. MS related symptoms are not to be reported as AEs unless, in the opinion of the investigator, the symptoms are unusually serious and relevant.

Vital Signs

Vital signs including body temperature, pulse, respiration rate, systolic and diastolic blood

pressure, and weight will be obtained at every visit

12-lead ECG

A 12-lead standard ECG will be performed at screening visit.

Clinical Laboratory Parameters

The following laboratory assessments will be performed at the local laboratory at selected visits:

- CBC
- Urinalysis
- CMP
- TSH
- Pregnancy Test (for female subjects only)

Adverse Event

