An adverse event (AE) is any unfavorable or unintended sign, symptom, or disease that is experienced by a subject who has received an investigational drug, whether or not there is a causal relationship with the investigational drug. At the signing of the informed consent form, each subject will be given the names and telephone numbers of investigational site personnel for reporting adverse events and medical emergencies. The investigator must conduct thorough assessment to determine the severity of the AE and the relationship to the study drug. Any clinically significant AE of severity moderate or higher, requires follow up until resolution or stabilization.

Serious Adverse Events

A serious adverse event (SAE) is defined as any event that:

- Results in the outcome of death
- Places the subject at immediate risk of death (a life-threatening event)
- Results in a congenital anomaly/birth defect
- Results in hospitalization or prolongs an existing hospitalization
- An event that results in persistent or significant disability/incapacity.
- Require intervention to prevent permanent impairment or one of the other outcomes listed in the definition above.

Adverse Event Recording/Reporting

All adverse events (including pre-dosing and treatment-emergent) should be recorded in the subject's Adverse Event CRF regardless of severity or relationship to study drug. The investigator must review the laboratory findings and sign and date the laboratory report. Any moderate or severe laboratory abnormalities should be reported to the coordinating center as outlined below. All SAEs must be reported by the investigator to Providence Regional Research/ Regulatory office by email at [contact] or fax to [contact] within 24 hours of the investigator's knowledge of the event. Providence Health & Services will report SAEs to the FDA. All SAEs must be recorded on SAE forms and be reported, whether or not the event is considered by the investigator to be related to study drug.

Severity

The intensity of severity of an AE will be graded as follows:

Mild	Symptoms(s) barely noticeable to subject or does not make subject uncomfortable; does not influence performance or functioning; prescription drug not ordinarily needed for relief of symptoms(s) but may be given because of personality of subject

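### The exemption of MS-related symptoms from AE reporting conflicts with the rules on relapses and worsening, so non-serious relapses and neurological worsening may be recorded inconsistently and under-counted

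*Combined protocol and SAP*

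**What the plan says.** Five statements in the protocol bear on whether a relapse or a neurological worsening becomes an adverse event.

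- Section D, Members and Responsibilities of DSMB: "The DSMB will review all adverse events (including all MS relapses) that occur during the study".
- Section D, Physical Examination: "Any worsening or new abnormality that is clinically significant is to be recorded as an AE and will be analyzed as such".
- The next sentence of that paragraph: "MS related symptoms are not to be reported as AEs unless, in the opinion of the investigator, the symptoms are unusually serious and relevant".
- Section D, Adverse Event: "An adverse event (AE) is any unfavorable or unintended sign, symptom, or disease that is experienced by a subject". No exception for MS is made. Adverse Event Recording/Reporting then asks for all AEs on the CRF "regardless of severity or relationship to study drug".
- Section C, Discontinuation of Subjects from the Study: "A relapse is defined as a new symptom, or worsening of pre-existing neurologic symptoms, of at least 24 hours duration", with further conditions on prior stability and on fever, sleep deprivation and emotional stress. A relapse is listed there as a reason for ending participation.

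The Statistical/Analytical Plan describes one safety output: AEs coded by organ system and tabulated by severity, relationship, treatment group and site. It mentions no relapse count or relapse table.

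**The concern.** A relapse, as the protocol defines it, consists of MS-related symptoms. A site that applies the exemption literally leaves a mild or moderate relapse off the AE CRF. A site that follows the DSMB paragraph or the general recording rule enters it. Both can claim to be following the protocol.

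Safety and tolerability of twice-weekly ACTH is a stated secondary endpoint, and the Background says that, to the authors' knowledge, this regimen has not been used before in MS patients. An event kept off the AE CRF leaves the only between-arm safety comparison that is planned, and nothing in the text says how it would otherwise reach the DSMB. The exemption also asks the investigator to decide that a symptom belongs to MS before recording it, whereas the AE definition applies whether or not the drug is thought to be the cause.

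**Working it through.** No arithmetic settles this point. The check is to take each kind of event and see what each rule requires.

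| Event | DSMB paragraph | Worsening sentence | Exemption sentence | AE recording rule | Other stated route |
|---|---|---|---|---|---|
| Stable, pre-existing MS symptom | Not named | Not an AE | Not an AE | Not clearly engaged | None needed |
| Relapse meeting an SAE criterion | AE | AE | AE if judged unusually serious and relevant | AE | SAE form, reported within 24 hours |
| Non-serious relapse | AE | AE if clinically significant | Not an AE unless judged unusually serious and relevant | AE | Ends participation |
| Clinically significant worsening outside the relapse definition (for example with fever) | Reviewed only if recorded as an AE | AE | Not an AE if attributed to MS, unless judged unusually serious and relevant | AE | None stated |

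The first two rows cause no practical difficulty. The conflict lies in the last two.

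**Is there a precedence rule?** None was found. The exemption directly follows the worsening sentence, so it can be read as qualifying it or as dealing only with background symptoms. Its threshold is undefined: it is neither the SAE definition nor one of the three severity grades (mild, moderate, severe).

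**Is there another route?**

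1. *Termination.* "Patient has a relapse during the study" is a termination criterion, and "If discontinuation of study drug occurs, a premature termination visit must be performed as soon as possible". That visit includes a neurological examination and an AE review, so the site should know of the relapse. Whether it is then written down as an AE is again subject to the exemption. No text sends termination reasons to the DSMB or compares them by arm. The visit is tied to stopping study drug, so it does not clearly apply in the 28 − 24 = 4 weeks after the last dose, although the week 28 visit has its own AE review.
2. *Patient contact.* Patient Monitoring and Evaluation tells patients to contact the treating neurologist at once about a relapse. No onward reporting is described.
3. *Disability scale.* The Study Flowchart lists EDSS at screening only. The neurological examination is repeated at every visit, but no on-study disability score would show worsening that had not been recorded as an event.

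**What does under-counting do to the comparison?** Let *a* and *b* be the true numbers of non-serious relapses in the two arms, and *p* the share entered as AEs. Assume that *p* is the same in both arms, which the blinding of investigators makes reasonable. The expected recorded difference is *pa* − *pb* = *p*(*a* − *b*). For any *p* below 1 the difference shrinks in absolute terms, while the ratio *pa*/*pb* = *a*/*b* is unchanged. Neither *p* nor the relapse rate is given, so no figure can be attached. If *p* varies among the five sites, the AE tables by site will partly reflect reporting habits.

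**The case against.** The strongest reply is that the text can be read in harmony. A relapse is a defined event, and the DSMB paragraph expressly places all relapses among the AEs. The worsening sentence makes clinically significant worsening an AE. The exemption then covers only everyday background MS symptoms. Relapses are also hard to overlook at a site, since they end participation, and any relapse meeting an SAE criterion is reported in any case. The CRFs are not part of the documents, so a relapse field may exist. Investigators are blinded, and fatigue, depression, sleepiness and suicidality are measured by instrument at every visit whatever the AE coding.

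Much of this stands, and it rules out several stronger readings that a reader might infer:

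- *That every relapse short of unusually serious will be missing from the AE tables.* This would need the general exemption to override the specific statement about relapses, which the documents do not say. SAE reporting and the AE review at the termination visit also count against it.
- *That worsening outside the relapse definition is recorded nowhere.* The worsening sentence is an express AE rule for it and carries no condition about fever or sleep deprivation.
- *That the safety comparison is biased towards one arm.* Blinding makes filtering with knowledge of the arm unlikely. Under-counting in both arms is the likelier result.
- *That the exemption should simply be deleted.* Patients enter with high fatigue scores and fatigue is the primary outcome, so full deletion would risk logging background fluctuation, and possibly the efficacy outcome, as AEs.

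What the reply does not remove is that the harmonised reading has to be supplied by the reader. The protocol does not state it, the exemption as worded is not limited to background symptoms, and no route to the DSMB or relapse table is given.

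**Conclusion.** The point holds in a limited form. The rules on MS-related symptoms, relapses, worsening and AE recording contradict one another for non-serious relapses and for clinically significant neurological worsening, and must be reconciled. As written, capture of these events depends on site judgement, so the AE tables by arm and the DSMB review can under-count them.

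The size is unknown: the protocol gives no relapse rate and no basis for estimating the share recorded. The conclusion assumes that at least some sites would apply the exemption as worded, and that no unseen form or instruction already settles the matter. It does not touch the efficacy analysis or SAE reporting. The change is worth making because it is cheap and improves a stated safety endpoint.

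**What to change.** Reconcile Discontinuation of Subjects from the Study, Physical Examination, Members and Responsibilities of DSMB, and Adverse Event Recording/Reporting as follows:

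1. Limit the exemption to stable, pre-existing MS symptoms.
2. State that every protocol-defined relapse and every clinically significant neurological worsening is recorded on the AE CRF with an MS-related yes/no flag.
3. State that these events are sent to the DSMB, and by what route.
4. In the Statistical/Analytical Plan, add a table of relapses by arm, and show the AE tables with and without flagged events.

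The cost is one CRF field, some extra data entry, and somewhat higher AE counts in both arms. The paired tables let a reader see how much of that rise comes from flagged events.
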